### **Quality Control**

The slide set distributed to each of the three expert pathologists incorporates control slides representing a randomly selected sample of screening slides; 10% of normal subjects and subjects excluded for the diagnosis of hyperplasia or cancer, to ensure quality control. The analysis of quality control is outside of the scope of this SAP.

#### **7.7.1.13 Vaginal Bleeding and/or Spotting**

Absence or occurrence of vaginal bleeding and/or spotting on a daily basis will be assessed using the scale below:

- 0 = Absence of vaginal bleeding or spotting;
- 1 = Spotting: evidence of minimal blood loss requiring none or at most one pad, tampon or panty liner per day;
- 2 = Bleeding: evidence of blood loss requiring more than one pad, tampon or panty liner per day.

Frequency counts (n) and percentage of subjects with absence of any bleeding and/or spotting during the cycle, with vaginal bleeding and/or spotting during the cycle, with bleeding only during the cycle, with spotting only during the cycle will be provided for each 28- day cycle of treatment based on data in the subject diary (in non-hysterectomized subjects) for the Safety Analysis Set.

The number of days with bleeding or spotting, as reported on subject diaries, will be summarized by 28-day cycle of treatment.

A listing will be provided for vaginal bleeding and/or spotting and/or amenorrhea for the Included Set.

The following data will be excluded from analysis of endpoints for bleeding (to be analysed separately)

- bleeding for the day on which an endometrial biopsy was performed and 6 days after biopsy and
- bleeding reported after discontinuation of study drug (for example withdrawal bleeding, on P4 treatment)

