6.2.2. Secondary Objectives and Endpoints

1. To evaluate the effect of treatment with E4 20 mg on lipid and glucose metabolism

Efficacy endpoints for secondary objective #1

- 1.1. Change from baseline to week 12 and week 52 in triglycerides, HDL-cholesterol, LDL-cholesterol, total cholesterol, lipoprotein(a), total cholesterol/HDL-cholesterol ratio, fasting glycemia, insulin, glycated hemoglobin, and HOMA-IR

2. To evaluate the effect of treatment with E4 20 mg on HRQoL and TS

Efficacy endpoints for secondary objective #2

- 2.1. Change from baseline to week 12 and week 52 in HRQoL using the MENQOL questionnaire
- 2.2. Total score in TS after 4 weeks, 12 weeks, and 52 weeks of treatment using the CGI questionnaire

3. To evaluate the effect of treatment with E4 20 mg on the endometrium in non-hysterectomized subjects

Safety endpoints for secondary objective #3

- 3.1 Change from baseline to each measured time point in endometrial thickness measured by ultrasound
- 3.2 Frequency of subjects in the different endometrial categories according to the Blaustein's pathology (see Appendix 16.3)
4. To evaluate the effect of treatment with E4 20 mg on vaginal bleeding in non-hysterectomized subjects

Safety endpoints for secondary objective #4

- 4.1 Frequency of women with vaginal bleeding and/or spotting during each 28-day cycle of treatment with E4 based on data in the patient diary
- 4.2 Number of days with bleeding and/or spotting during each 28-day cycle of treatment based on data in the patient diary
- 4.3 Frequency of women with amenorrhea (absence of any bleeding or spotting) during each 28-day cycle of treatment with E4 based on data in the patient diary
- 4.4 Cumulative rates of amenorrhea defined as the percentage of women who reported consecutive cycles of amenorrhea for a given cycle of time

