10.4.8. Endometrial Biopsy in Non-hysterectomized Subjects

Endometrial biopsies will be used for the evaluation of endometrial safety of non-hysterectomized subjects participating in the trial. An endometrial biopsy will be performed for all non-hysterectomized subjects at screening (Visit 1), at the EoT Visit (Visit 7 in the Efficacy Study part and Visit 6 in the Safety Study part) or upon early termination providing that the subject has been treated with E4 or placebo for at least 12 weeks.

Additional unscheduled endometrial biopsies will be performed in case a bi-layer endometrial thickness of >10 mm is detected on TVUS and/or in the presence of persistent and/or recurrent bleeding, confirmed by the investigator.

Detailed procedures for obtaining endometrial biopsies, tissue preparation and endometrial biopsy assessment will be described in separate study manuals to be provided to the sites, a summary is provided below.

Procedure for obtaining endometrial biopsy

The endometrial biopsy should be taken according to local procedures by a board-certified gynecologist or designee, preferably using the Pipelle technique. The “Pipelle de Cornier” is internationally used for endometrial biopsies, because it is adequate and safe. However, comparable devices may exist and be used, providing that they are adequate for sampling and not traumatizing. The screening biopsy should have sufficient endometrial tissue for diagnosis. If insufficient tissue specimen or if no tissue is obtained, the endometrial biopsy may be repeated once.

Subjects can be given sedation and/or pain relief prior to the procedure under standard local care providing that the medications are not listed as unauthorized therapies in Section 9.6.2. and as per Investigator judgment. Women will receive counselling to include discharge instructions and to expect mild to moderate bleeding that can last for a few days and will be advised to call the site if they experience fever, pain or increased or prolonged bleeding. If an abnormal uterine bleeding occurs within 10 weeks after a first normal endometrial biopsy, a thorough gynecological examination, a TVUS, and – if necessary – a second endometrial biopsy will have to be performed.

Evaluation of endometrial tissue

The endometrial tissue obtained by endometrial biopsy at screening, during the conduct of the study, and at the end-of-study will be processed in the same manner by a central laboratory.

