 For non-hysterectomized (NH) subjects endometrial thickness will be measured after 3, 6, 9 and 12 months (Visits 4, 5, 6 and 7 of the Efficacy Study part and Visits 3, 4, 5 and 6 of the Safety Study part respectively) of treatment by TVUS and subjects will record daily the vaginal bleeding events. If after the first 4 weeks of treatment a subject presents with a bi-layer endometrial thickness >10 mm as assessed by TVUS or presents with persistent and/or recurrent bleeding, confirmed by the investigator, an endometrial biopsy will be performed. If the biopsy shows hyperplasia or worse, the study drug will be discontinued, and the subject will be withdrawn from the study. The subject will be treated with P4 200 mg once daily for 14 days. If the endometrial event has not resolved, treatment with a progestin will be started according to local practice/guidelines. All NH subjects will receive treatment with 200 mg P4 for two weeks after completion of E4 treatment.

Before Protocol Version 7.1 (Amendment 6.1) disordered proliferative endometrium was considered as a reason for the exclusion or discontinuation of the subject from the study.

At the Washout visit, after signing the informed consent form (ICF), the inclusion and exclusion criteria will be checked as well as the prior medication list. If a subject uses medication prohibited by the protocol, then this subject will be asked to stop this medication. After a variable washout period (depending on type of prior medication) the subject will be asked to return to start screening. The Washout and screening visits may occur at the same time for subjects who do not use prohibited medication. Subjects who do not fulfill the VMS requirements for participation in the Efficacy Study part, may participate in the Safety Study part, providing that they meet all other inclusion and exclusion criteria.

The screening period requires at least one visit, to occur as per protocol, at the beginning of the period, but some assessments (e.g., mammography, biopsy, transvaginal ultrasound [TVUS], ECG and Papanicolaou [PAP] test) may require additional visits if these assessments cannot be completed during the same visit.

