**Table 1: Derived Variables**

Variables	Formula																								
Demographic and Baseline Characteristics																									
Body mass index (BMI) (kg/m  )	weight (kg)/[height (m)] 																								
Study Treatment																									
Treatment Start Date	The date of first dose of study drug.																								
Treatment Stop Date	The date of last dose of study drug.																								
Duration of exposure (Days)	(Treatment Stop Date – Treatment Start Date) + 1																								
Treatment compliance (%)	100 x [(total number of tablets dispensed) – (total number of tablets returned)]/(duration of exposure in days)																								
Study Day	Prior to Treatment Start Date: Date of interest – Treatment Start Date  On or after Treatment Start Date: Date of interest – Treatment Start Date + 1																								
Study Week	
Study Week is defined as follows for the first 7 weeks
 
  
 Week	Start (Study Day)	End (Study Day)	
   
 1	1	7	
 
 2	8	14	
 
 3	15	21	
 
 4	22	28	
 
 5	29	35	
 
 6	36	42	
 
 7	43	49	
  
	Week	Start (Study Day)	End (Study Day)	1	1	7	2	8	14	3	15	21	4	22	28	5	29	35	6	36	42	7	43	49
Week	Start (Study Day)	End (Study Day)																							
1	1	7																							
2	8	14																							
3	15	21																							
4	22	28																							
5	29	35																							
6	36	42																							
7	43	49																							

Study Cycle	28-day period starting from Treatment Start Day
Adverse Events	
Adverse Event (AE) Start Day	Prior to Treatment Start Date: AE start date – Treatment Start Date  On or after Treatment Start Date: AE Start Date – Treatment Start Date + 1
AE Stop Day	Prior to Treatment Start Date: AE stop date – Treatment Start Date  On or after Treatment Start Date: AE stop date – Treatment Start Date + 1
AE Duration (Days)	(AE Stop Date – AE Start Date) + 1

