### 7.7.1.14 Amenorrhea

Subjects with amenorrhea (absence of any bleeding or spotting) during each 28-day cycle of treatment with E4 (after exclusion the bleeding reported on the day of biopsy and 6 days after biopsy, or after discontinuation of study drug) will be summarized by using frequency count and percentages based on subject diary (in non-hysterectomized subjects) for the Safety Analysis Set.

Cumulative rates of amenorrhea will be defined as the percentage of women who reported consecutive cycles of amenorrhea for a given cycle of time. For example, if a subject had no bleeding or spotting from Study Day 1 to Study Day 364, then this subject has cumulative amenorrhea from the 1st to 13th cycle. The number and percentage of subjects with amenorrhea for each cumulative period will be summarized separately for the 1st to 13th cycle, 2nd cycle to 13th cycle, ...., and the 13th cycle.

Cumulative ‘no bleeding’ will be defined as the percentage of women who reported consecutive cycles without bleeding for a given cycle of time. For example, if a subject had no bleeding from Day 1 to Day 364, then this subject has cumulative no bleeding from the 1st to 13th cycle. The number and percentage of subjects with ‘no bleeding’ for each cumulative period will be summarized separately for the 1st to 13th cycle, 2nd cycle to 13th cycle, ...., and the 13th cycle.

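### The 7-day post-biopsy exclusion in the Safety-part bleeding analysis also removes bleeding already under way, and can turn the tail of an ongoing episode into an amenorrheic cycle

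*SAP*

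**What the plan says.** Protocol 6.2.2, secondary objective 4 of the Safety Study part, sets four diary endpoints by 28-day cycle. One is "Number of days with bleeding and/or spotting during each 28-day cycle of treatment based on data in the patient diary"; the others are the frequency of women with bleeding or spotting, the frequency of amenorrhea, and cumulative amenorrhea. Neither that section nor Protocol 12.8 excludes days around a biopsy.

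SAP 7.7.1.13 adds an exclusion. Its lead-in is "The following data will be excluded from analysis of endpoints for bleeding (to be analysed separately", and the first item is "bleeding for the day on which an endometrial biopsy was performed and 6 days after biopsy". The second item is bleeding after study drug has been stopped. SAP 7.7.1.14 defines amenorrhea per cycle with the same carve-out: "after exclusion the bleeding reported on the day of biopsy and 6 days after biopsy, or after discontinuation of study drug". No distinction is made between scheduled and unscheduled biopsies, or between bleeding that starts after the biopsy and bleeding already present.

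Unscheduled biopsies have stated triggers. SAP 3.1 (footnote to Figure 1) calls for one if, after the first 4 weeks, a woman "presents with a bi-layer endometrial thickness >10 mm as assessed by TVUS or presents with persistent and/or recurrent bleeding, confirmed by the investigator". Protocol 10.4.8 likewise requires additional biopsies above the same thickness limit and/or "in the presence of persistent and/or recurrent bleeding, confirmed by the investigator".

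SAP section 8 lists three changes from the protocol, all about analysis sets. The biopsy exclusion is not among them.

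**The concern.** A post-biopsy exclusion is meant to remove an artefact. Here the event that opens the exclusion window is often the outcome itself: a woman is biopsied because she is bleeding, and the biopsy day and the next 6 days of that bleeding are then taken out of the endpoint.

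The error has one direction. The SAP removes the bleeding but does not say that the days become non-evaluable or that the cycle leaves the denominator. As 7.7.1.14 reads, a cycle with no bleeding left after the exclusion is amenorrheic. Bleeding-day counts can therefore only fall, and amenorrhea and the cumulative rates can only rise. At stake is the description of bleeding on E4 20 mg given without concurrent progestin in women with a uterus, which is a named secondary safety objective.

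**Working it through.** **Step 1. The cycle frame.** A study cycle is a "28-day period starting from Treatment Start Day". SAP 7.7.1.14 illustrates 13 cycles by a woman "if a subject had no bleeding or spotting from Study Day 1 to Study Day 364". Check: 13 × 28 = 364, which agrees. For study day d, cycle(d) = floor((d − 1)/28) + 1.

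**Step 2. Which biopsies the rule reaches in cycles 1 to 13.**
- *End of treatment.* The visit window is Day 365 to 371 (SAP Table 5). cycle(365) = floor(364/28) + 1 = 14 and cycle(371) = floor(370/28) + 1 = 14. The last dose is taken the evening before the visit (Protocol 10.1.6.6), so the item on stopped study drug already removes this bleeding.
- *Screening.* The biopsy matters only if taken within 6 days before Day 1. It must first be processed centrally and read before inclusion (Protocol 10.4.8), so this should be uncommon.
- *Early termination.* It matters only if taken while the woman is still on drug.
- *Unscheduled.* These are the bulk of what remains, and they follow bleeding or a thick endometrium.

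**Step 3. Days removed per biopsy.** Take a continuous episode of L days biopsied on its day b (b at least 2). Days removed = min(7, L − b + 1). The maximum is 7 of 28 days, or 25% of a cycle.

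**Step 4. Cycles turned to amenorrhea.** Days before b are kept, so the cycle holding them still counts as bleeding. A cycle is lost only if it starts on one of episode days b to L and no bleeding remains after the window. With the episode start uniform over the 28 cycle days, the chance is (L − b + 1)/28 when L − b + 1 is 7 or less. It is 0 when the episode outlasts the window.

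| Episode length L | Biopsy on day b | Days removed | Share of episode | Chance a cycle becomes amenorrheic |
|---|---|---|---|---|
| 10 | 4 | min(7, 7) = 7 | 70% | 7/28 = 25% |
| 10 | 8 | min(7, 3) = 3 | 30% | 3/28 = 11% |
| 14 | 8 | min(7, 7) = 7 | 50% | 7/28 = 25% |
| 21 | 8 | min(7, 14) = 7 | 33% | 0/28 = 0% |

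The lengths and biopsy days are illustrative; the documents give none.

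**Step 5. Cohort scale.** About 200 non-hysterectomized women are planned (SAP 3.1). The trigger applies after the first 4 weeks, which leaves cycles 2 to 13, that is 12 cycles: 200 × 12 = 2400 woman-cycles. With the anticipated 50% drop-out (Protocol 8.1) spread evenly, 2400 × 0.75 = 1800. The biopsy rate is not given, so I assume that 5%, 15% or 30% of women have one such biopsy: 10, 30 or 60 biopsies.
- At 25% per biopsy: 2.5, 7.5 or 15 cycles, from 2.5/2400 = 0.10% to 15/1800 = 0.83% of woman-cycles.
- If every biopsy turned one cycle: from 10/2400 = 0.42% to 60/1800 = 3.33%. This needs cycles whose only bleeding lies in the window with none before the biopsy, and that bleeding may be procedural.

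**The case against.** The best defence is that the exclusion has a documented basis. Protocol 10.4.8 has women counselled that some bleeding may follow the procedure for a few days. Where a biopsy was prompted by thickness alone and no bleeding preceded it, the rule removes artefact, which is correct. The diary cannot separate the two sources in a woman already bleeding, so keeping her days counts some procedural bleeding as drug effect. This stands, and it is why replacing the current rule outright is not the remedy.

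The excluded data are also to be analysed apart, bleeding is listed by subject, and grade 2 bleeding is reported and tabulated as an adverse event of special interest. These help but do not repair the endpoint. The separate analysis has no method, table or denominator. The adverse event route misses spotting, does not count days, and started only with approval of protocol version 6.0, without retrospective reporting. A listing gives no rate.

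A reader might infer that the rule erases the outcome in the women most affected. The documents do not support that. Bleeding before the biopsy and after the window stays in, and the longest episodes lose no cycle at all (the 21-day row above). A reader might also infer a distorted comparison between arms in the Efficacy Study part. This SAP covers only the open-label single arm, and the separate Efficacy SAP is not among the documents, so nothing can be said about its rule.

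**Conclusion.** The point holds in a limited form. The exclusion is partly outcome-dependent and pushes bleeding days down and amenorrhea up. Per biopsied ongoing episode, up to 7 bleeding days are lost, and the chance of a falsely amenorrheic cycle runs from 0 to 25%. Across the Safety part the effect is probably small, roughly 0.1 to 0.8% of woman-cycles at the 25% rate. That range rests on assumed biopsy rates of 5 to 30%, one biopsy per woman, continuous episodes and uniform timing. No test or power is affected, since the analysis is descriptive.

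It remains more than missing detail: the stated rule puts a woman in mid-episode among the amenorrheic for a cycle in which she bled, and it departs from the protocol endpoints without being declared. The reading that excluded days count as bleed-free is the natural one of 7.7.1.14, though the SAP does not say so outright.

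**What to change.** 1. In SAP 7.7.1.13 and 7.7.1.14, do not class a cycle as amenorrheic or as without bleeding when its only bleeding lies in the exclusion window and belongs to an episode that began before the biopsy. State that excluded days are non-evaluable, not bleed-free, and what this does to the cycle denominator.
2. Make the separate analysis concrete: produce the bleeding-day, amenorrhea and cumulative tables twice, once with the current exclusion and once keeping the days of episodes under way at biopsy. Define when an episode is under way. Bleeding or spotting on the day before the biopsy is the simplest test, but it misses women with recurrent bleeding who were dry that day, so it should not be the only result shown.
3. List the exclusion in SAP section 8 as a change from the protocol endpoints.

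The cost is SAP wording, one derivation flag and a second set of tables, from diary and biopsy dates already collected. The downside is that the retained version counts some procedure-related days in women who were already bleeding.

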### 7.7.1.14 Amenorrhea

Subjects with amenorrhea (absence of any bleeding or spotting) during each 28-day cycle of treatment with E4 (after exclusion the bleeding reported on the day of biopsy and 6 days after biopsy, or after discontinuation of study drug) will be summarized by using frequency count and percentages based on subject diary (in non-hysterectomized subjects) for the Safety Analysis Set.

Cumulative rates of amenorrhea will be defined as the percentage of women who reported consecutive cycles of amenorrhea for a given cycle of time. For example, if a subject had no bleeding or spotting from Study Day 1 to Study Day 364, then this subject has cumulative amenorrhea from the 1st to 13th cycle. The number and percentage of subjects with amenorrhea for each cumulative period will be summarized separately for the 1st to 13th cycle, 2nd cycle to 13th cycle, ...., and the 13th cycle.

Cumulative ‘no bleeding’ will be defined as the percentage of women who reported consecutive cycles without bleeding for a given cycle of time. For example, if a subject had no bleeding from Day 1 to Day 364, then this subject has cumulative no bleeding from the 1st to 13th cycle. The number and percentage of subjects with ‘no bleeding’ for each cumulative period will be summarized separately for the 1st to 13th cycle, 2nd cycle to 13th cycle, ...., and the 13th cycle.

## 7.8 Subgroup Analysis

Summary tables will also be presented by hysterectomy status (hysterectomized and non-hysterectomized) as detailed in the respective statistical methods sections.

## 7.9 Interim Analysis

Not applicable

---

**8        CHANGES    TO    PLANNED    ANALYSIS    FROM    STUDY**  
**PROTOCOL**

- The Endometrial Safety Analysis Set, defined in protocol section 12.1, has been removed from SAP section 5; the endometrial analysis will be performed based on the Safety Analysis Set.
- The Intent-To-Treat (ITT) Set, defined in protocol section 12.1, has been removed from SAP section 5. The definition of the ITT and Safety Analysis Sets is same as this is an open label study and only one treatment group. The Safety Analysis Set will be the primary analysis population for the efficacy analyses.
- The modified Intent-To-Treat (mITT), defined in protocol section 12.1, has been removed from SAP section 5. The mITT was intended to be used in a sensitivity analysis of the primary efficacy endpoint, which is not relevant for the Safety Part of the study.

---

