7.2. Study and Treatment Assignment

Assignment into any of the study parts (i.e. Efficacy and Safety) and treatment subgroups (15 mg, 20 mg and placebo) will be done by the Interactive Web Response System (IWRS) system (i.e cannot be done by site staff). This assignment will take into account the modified MENQOL score, frequency and severity of hot flashes, hysterectomized vs. non-hysterectomized status, and availability of places in each study part/subgroup.

Efficacy Study part

Subjects eligible for participation in the Efficacy Study part will be randomly allocated to one of the three treatment arms [E4 15 mg (Arm 1), E4 20 mg (Arm 2) or placebo (Arm 3)] in a 1:1:1 ratio using a computer-generated randomization schedule.

Safety Study part

Subjects eligible for participation in the Safety Study part will all be allocated to treatment with E4 20 mg (Arm 4).

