12. STATISTICAL METHODS

12.1. Statistical populations

Analyses will be based on the Enrolled Set, the Safety Analysis Set, the Intent-to-treat (ITT) Set, the Endometrial Safety Analysis Set, the Per-protocol (PP) Set and the modified Intent-to-treat (mITT) Set. The definitions of the analysis sets, with the exception of the mITT, follow those given in the ICH E9 guideline (CMP/ICH/363/96).

Enrolled Set: All subjects who sign the ICF form the Enrolled Set.

Safety Analysis Set: Randomized subjects who receive at least one dose of randomized study medication form the Safety Set. The Safety Analysis Set will be used for all analyses of safety, tolerability, and background characteristics and all analyses on this set will be based on treatment received.

Endometrial Safety Analysis Set: All randomized subjects who received at least one dose of randomized study medication, had an evaluable biopsy at Baseline and at Month 12 (defined by a Visit window as on or after Day 326) or had a diagnosis of endometrial hyperplasia prior to Month 12.

Intent-to-treat (ITT) Set: The ITT Set consists of all randomized subjects who receive at least one dose of randomized study medication. The ITT Set will be the primary analysis population for the efficacy analyses and all analyses on this set will be based on randomized treatment.

Modified Intent-to-treat (mITT) Set: The mITT Set consists of all randomized subjects in the ITT Set excluding subjects presenting at least one of the following features:

- At least one post baseline E4 concentration level below the lower limit of quantification
- At least one post screening E2 concentration level is superior to 40 pg/mL

Per-protocol (PP) Set: Subjects in the ITT Set who do not have major protocol deviations will form the PP Set. The major protocol deviations will be defined at the time of the evaluability assessment between the database soft lock and hard lock before unblinding. The PP Set will be used for efficacy sensitivity analyses and all analyses on this set will be based on randomized treatment.

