12.8. Safety parameters (safety set)

All safety parameters will be summarized using data from the Safety Analysis Set if not indicated otherwise. No formal statistical test will be performed to determine statistical significance between treatment groups. Continuous variables will be summarized using descriptive statistics (N, mean, standard deviation, median, minimum, maximum), categorical variables will be presented in frequency tables using counts and percentages. The frequency of endometrial events will be computed on the evaluable biopsies of the endometrium. The incidence of spotting/bleeding will be analyzed by a 28-day period. The incidence rate of endometrial events will be computed on the evaluable endometrium. The 95% two-sided CI will be computed on the observed frequency of hyperplasia/carcinoma of the endometrium.

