## 7 STATISTICAL METHODS

### 7.1 General Statistical Conventions

All statistical procedures will be completed using SAS version 9.4 or higher, there is only one treatment group, thus no formal statistical analysis will be performed.

Confidence intervals (CIs) will be presented as 2-sided 95% CIs unless specified differently in specific analysis.

Categorical variables will be summarized using frequency counts (n) and percentages in each category, percentages will be computed for subjects with non-missing value (as the denominator). If there are missing values, missing values counts will be provided. All percentages will be rounded to one digit after decimal point. The frequency counts and percentages will be presented in the form XX (XX.X %), where the percentage is in the parentheses. If the percentage of a category is '100 %', then it will be displayed as '100 %' (no decimals will be added after 100).

Continuous variables will be summarized using the number of subjects with non-missing values (n), mean, median, standard deviation (SD), minimum (min), maximum (max) and missing values counts. Missing values counts will be displayed only if there are missing values. All mean and median values will be formatted to one more decimal place than the measured value. Standard deviations will be formatted to two more decimal places than the measured value. The min and max will be displayed to the same number of decimal places as the measured value. Unscheduled visits will not be summarized in tables.

Analyses will be performed by visit, irrespective of any time window deviations, unless otherwise specified. The early discontinuation (ED) visit will be separated from the scheduled EoT- visit based on discontinuation reason. Unscheduled visits related to efficacy data will be clustered with scheduled visits based on the visit windows in [Table 5](#) of Appendix 1. Similarly, the unscheduled visit results will be clustered with scheduled visits based on the visit windows defined in [Table 6](#) (Appendix 1) for microscopic findings and laboratory endpoints and endometrial biopsy. Similarly, the scheduled visits for ECG, Procedures, Questionnaire, Vital Signs, Imaging and Findings will be based on visit window [Table 7](#) in Appendix 1.

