**Table 6: Visit Window Microscopic Findings and for Laboratory Endpoints**

Assessment Visit	Time window	Visit
Safety Visit 2		Week 5
Safety Visit 3		Week 13
Safety Visit 4		Week 29
Safety Visit 5		Week 41
Safety Visit 6/EoT		Week 53 (if discontinuation reason is missing in DS domain) Early Discontinuation (if discontinuation reason is non-missing in DS domain)
Safety Visit 7 Follow-up		Week 55/56 Follow-up
Unscheduled Visits	<0, 2 to 18	Unscheduled
	1	Visit 1 Baseline
	19 to 46	Week 5
	47 to 74	Week 9
	75 to 144	Week 13

	145 to 242	Week 29
	243 to 325	Week 41
	326 to 375*	Week 53
	>=327#	Week 53
	>=376*	Week 55/56 Follow-up

Note: \*only for non-hysterectomized subjects; #: only for hysterectomized subjects

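### SAP section 8 drops the protocol's Endometrial Safety Analysis Set without a reason, and no table described in the SAP gives a 12-month rate of hyperplasia or carcinoma

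*SAP*

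**What the plan says.** Protocol 12.1 defines the set as "All randomized subjects who received at least one dose of randomized study medication, had an evaluable biopsy at Baseline and at Month 12", with Month 12 meaning Day 326 or later, "or had a diagnosis of endometrial hyperplasia prior to Month 12". Amendment 6.1 added the set, and the SAP states that it is based on the protocol version which that amendment produced.

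SAP section 8 reports that the set "has been removed from SAP section 5; the endometrial analysis will be performed based on the Safety Analysis Set". The next two bullets, on the ITT and mITT sets, each give a reason. This one does not, and none appears in the revision history, SAP section 5 or SAP 7.7.1.12.

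Protocol 12.8 does not name the set. It says: "The frequency of endometrial events will be computed on the evaluable biopsies of the endometrium".

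SAP 7.7.1.12.2 describes two summaries of the Final/Consensus diagnosis on the Safety Analysis Set: one by on-treatment visit, and one of each woman's worst result across all on-treatment visits, unscheduled ones included. For the by-visit summary, SAP 7.1 states: "The early discontinuation (ED) visit will be separated from the scheduled EoT- visit based on discontinuation reason". Appendix 1, Table 6 accordingly labels a Visit 6 record "Early Discontinuation (if discontinuation reason is non-missing in DS domain".

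**The concern.** The endometrial effect of E4 20 mg is a secondary objective of the Safety Study part. Protocol 7.1.3.2 extends treatment to 12 months because some effects may appear only after prolonged exposure. A reader will therefore look for the proportion of women with hyperplasia or carcinoma over 12 months of unopposed treatment.

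The protocol's set joins the two groups that bear on this: women biopsied at Month 12 and women diagnosed before it. Once it is removed, no described table makes that combination. With 50% dropout expected, women who leave early are a large group, so how they enter the denominator can move the reported rate. A reader is also not told why the set was removed.

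**Working it through.** **1. Who is counted where.** SAP 7.1 bases percentages on non-missing values and SAP 7.7.1.12 bases the rate on evaluable endometrium. I therefore read the worst-case denominator as women with at least one evaluable on-treatment biopsy.

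| Woman (biopsies evaluable) | Week 53 row | Worst-case table | Protocol set |
|---|---|---|---|
| Visit 6 biopsy at Week 53, no discontinuation reason | in | in | in |
| Hyperplasia before Day 326, withdrawn | out | in, as a case | in, as a case |
| Visit 6 biopsy on or after Day 326, discontinuation reason recorded | out | in | in |
| Benign exit biopsy after at least 12 weeks, before Day 326 | out | in | out |
| Benign for-cause biopsy after week 4, no later biopsy | out | in | out |

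Neither summary reproduces the last column.

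**2. The plan's own figure.** Protocol 8.1 expects about 200 completers among about 400 women at 50% dropout: 400 × (1 − 0.50) = 200, which agrees. Applying the same 50% to the roughly 200 non-hysterectomized women gives 100 Month 12 biopsies. Protocol 8.1 states this rate for the whole part, so its use here is an assumption.

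**3. Women with only an earlier biopsy (inputs assumed).** Let w be the share leaving by week 12, e the share of later leavers with an exit biopsy, and f the share of week-12 leavers with a for-cause biopsy. The number is 200 × (0.50 − w) × e + 200 × w × f.
- w = 0.45, e = 0.6, f = 0: 200 × 0.05 × 0.6 = 6.
- w = 0.25, e = 1, f = 0.1: 50 + 5 = 55.

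The 35% week-12 dropout that the protocol gives for non-hysterectomized women in the Efficacy part lies within this range of w.

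**4. Illustration.** Assume four cases, two before Day 326. Intervals are Clopper-Pearson 95%; the SAP names no method.
- Protocol set: 4/(100 + 2) = 3.9% (1.1 to 9.7).
- Worst-case table: 4/106 = 3.8% (1.0 to 9.4) to 4/155 = 2.6% (0.7 to 6.5).
- Week 53 row: 2/100 = 2.0% (0.2 to 7.0).

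With no cases the upper limit is 3.6% at n = 100, against 3.4% at n = 106 and 2.4% at n = 155.

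**5. Direction of error.** Assume a true 12-month risk r = 0.04, with a share p of cases found at onset and withdrawn. Completers are c = 0.50 and later leavers l = 0.50 − w, all treated as leaving before Day 326. Leaving times are uniform over weeks 0–12 and 12–53. G_w and G_l are the chances that onset precedes leaving in the two groups. Put A = l·r·G_l·[p + (1 − p)e] + w·r·p·G_w, q_l = r·p·G_l and q_w = r·p·G_w.
- Week 53 row = c·r·(1 − p) / (c − c·r·p)
- Worst case = (c·r + A) / {c + l[q_l + (1 − q_l)e] + w[q_w + (1 − q_w)f]}
- Protocol set = (c·r + A) / (c + A)

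Example: onset uniform over weeks 26–53, p = 0.5, w = 0.35, e = 1, f = 0. Then G_l = (27/41)/2 = 0.329, G_w = 0 and A = 0.15 × 0.04 × 0.329 = 0.00198.
- Week 53 row: 0.010/0.490 = 2.04%
- Worst case: 0.02198/0.650 = 3.38%
- Set: 0.02198/0.50198 = 4.38%

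I varied onset (weeks 0–53, or 26–53 after the six months mentioned in Protocol 5.1), p (0.25, 0.50, 0.75), w (0.45, 0.35, 0.25), e (0.6, 1) and f (0, 0.1). That is 2 × 3 × 3 × 2 × 2 = 72 combinations.

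| | Range | Mean absolute error | Largest error | Closer to 4% |
|---|---|---|---|---|
| Week 53 row | 1.0% to 3.0% | – | – | – |
| Worst-case table | 3.0% to 4.3% | 0.40 points | 0.99 | 36 of 72 |
| Protocol set | 4.1% to 5.3% | 0.56 points | 1.32 | 36 of 72 |

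The last two columns compare only the worst-case table and the set. Those two bracket 4% in 64 of the 72 combinations.

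**The case against.** The strongest reply is that no planned analysis has been lost. Protocol 12.1 defines the set, but Protocol 12.8 uses evaluable biopsies and, by default, the Safety Analysis Set. SAP 7.7.1.12 follows that almost unchanged. The endpoint is the frequency of women in each histologic category, which the SAP delivers with confidence intervals. The removal is disclosed. The protocol's wording also fits Arm 4 poorly: it speaks of randomized subjects, whereas Protocol 7.2 allocates everyone in this part to one treatment, and it admits early hyperplasia but not early carcinoma. All of this stands, and it limits the point to a missing reason and a missing rate.

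A reader might go further in three ways that the documents do not support:
- That early cases are concealed. They are counted in the worst-case table, early discontinuation has its own by-visit category, and the SAP lists every biopsy reading as well as the abnormal biopsies.
- That a prespecified analysis was deleted. No analysis is assigned to the set.
- That the set is the correct denominator and the worst-case table simply dilutes the rate. The set keeps early cases while excluding early benign exits, and it overstated the assumed risk in every combination. The worst-case table was no further from it on average.

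The table shells and the Efficacy part SAP are separate documents that were not available. They might contain such a table, but SAP section 8 does not suggest it.

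**Conclusion.** The point holds as a modest one. SAP section 8 removes a protocol-defined set without a reason, and the SAP describes no 12-month rate that combines early and Month 12 cases. The Week 53 row can fall well below the assumed risk (1.0% to 3.0% against 4%). The worst-case table mostly understates and the set overstates, so the two together are more informative than either alone.

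The two textual findings do not depend on the illustration. Its figures do rest on assumptions: every input except about 200 women and 50% dropout is assumed, the case counts are invented, and with so few cases all the intervals overlap. No success threshold is affected. This is a cheap improvement in reporting, not a threat to the trial's conclusions.

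**What to change.** - **SAP section 5.** Keep the set for Arm 4, defined as: *treated non-hysterectomized subjects with either (i) evaluable biopsies at baseline and at Month 12 (Day 326 or later, including Visit 6 biopsies with a recorded discontinuation reason), or (ii) a Final/Consensus diagnosis of hyperplasia or carcinoma after first dose and before Day 326.* Put no baseline-biopsy condition on limb (ii), because the protocol most naturally reads without one. Put no Day 375 cap on Month 12. The protocol has none, Table 6 applies that limit only to unscheduled visits, and SAP 7.1 says: "Analyses will be performed by visit, irrespective of any time window deviations, unless otherwise specified".
- **SAP section 8.** Replace the bullet. State that the set is kept, that the reference to randomization is dropped because Arm 4 is allocated, and that early carcinoma is added.
- **SAP 7.7.1.12.2.** Add one supplementary table of the hyperplasia/carcinoma rate with its 95% CI on this set, beside the Safety Analysis Set worst-case table. In a footnote, give the number of early benign exits excluded, and say that the set tends to overstate and the worst-case table to understate.

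If the sponsor still prefers to omit the set, section 8 should at least say why.

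The cost is one more table and wording in three places, from data already collected. The interval will be wider than in the worst-case table and the rate probably slightly less favourable.
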